The study population will consist of patients who have been diagnosed with KOA (i.e., ICD 10 diagnosis code M17) and have failed initial conservative treatment options. If the patient has bilateral KOA the patient would be excluded unless the patient had only unilateral symptoms. The study will not include patients who have end-stage KOA (i.e., Kellgren-Lawrence grade 4) for which surgical intervention would be more appropriate. Determining a Kellgren-Lawrence grade is a standard of care for diagnosing KOA and is done by reading a standing radiograph of the knee.

The clinic completes an average of approximately 630 office visits per month, 25% of which is related to the care of osteoarthritis. We anticipate that 50% of patients with KOA will satisfy inclusion and exclusion criteria and 80% of eligible patients will be willing to participate in the study. We anticipate enrollment of four patients per month over a maximum enrollment period of 16 months from the start date.

Number of Subjects to be included in the study: 45

We expect that up to 1 of every 3 patients consented will need to be withdrawn prior to the treatment intervention. Withdrawal criteria include use of NSAIDs or corticosteroids within 2 weeks prior to the treatment intervention date, or if a patient's platelet count is found to be <150,000 platelets per microliter of blood or >450,000 platelets per microliter of blood. Withdrawal criteria will be further discussed in section 2.4. We will apply the treatment intervention to only 30 total patients (i.e., n = 15 per treatment group); however, we anticipate consenting up to 45 patients based on possibility of withdrawal from the study. We will discontinue screening and consenting of patients if 30 patients have undergone one of the two treatment interventions.

As attrition following the treatment intervention is only expected to be due to a patient undergoing TKA prior to the 1 year follow-up or due to unforeseen illness, we do not anticipate this having an effect on our population. To further ensure visit compliance, compensation (i.e., a \$25 gift card) will be offered with completion of the 3, 6, and 12 month research follow-up visits.

Proposed Study Start Date: October 1, 2016

Proposed Study End Date: April 1, 2019

Inclusion Criteria:

- 1) Male and female patients 40 to 70 years old
- 2) Diagnosed with KOA based on the American College of Rheumatology criteria including symptomatic reports and radiographic findings

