Patients completing informed consent will be randomized in a 1:1 single-blinded fashion. The randomization allocation schedule will be developed by the research team member performing the statistical analyses and will not be shared with the remainder of the research team. Following the completion of informed consent and collection of baseline information for each patient, the research team member responsible for scheduling the treatment procedure will be made aware of group allocation. This research team member will assign a random number to each patient and independently maintain a key to be able to link the patient to the data collected as well as identify the group membership of each patient. This research team member will not be involved in the collection of 3 month, 6 month, or 12 month study variables. The designated research team member who will collect study variables at 3, 6, and 12 months will remain blinded to group allocation throughout the duration of the study. The primary investigator (i.e., the physician providing the treatment) will not be blinded to group allocation as knowledge of group allocation will be essential to deliver two distinctly different treatment procedures and to provide the participant with an explanation of the clinical procedure prior to initiating the treatment. However, the primary investigator will be unaware of the randomization allocation schedule. Randomization will be blocked to prevent selection and accidental bias while ensuring equal allocation to each treatment group.

Study Treatment/Interventions

After randomization, the patient will be scheduled for the treatment intervention within the next 30 days after the completion of informed consent and baseline procedures. All patients will be restricted from use of NSAIDs or oral corticosteroids for 2 weeks prior to the planned treatment procedure.

At the baseline visit, patients randomized to Group A (BMAC and PRP injections to target knee) will have venous blood sampled by the clinic staff in order to determine the patient's platelet count via a complete blood count (CBC) in the lab based on established procedures. Specifically, the venous blood will be drawn in a lavender-top ethylenediamine tetraacetic acid tube. The sample will be mixed by gently inverting 8 times. The sample will be sent to OhioHealth Laboratory Services and be received within 24 hours at ambient temperature.

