3. All patients will complete a follow up visit at approximately 6 months (+/- 14 days) following the date of the treatment provided for completion of the primary and secondary outcome tools.
4. All patients will complete a follow up visit at approximately 12 months (+/- 14 days) following the date of the treatment provided for completion of the primary and secondary outcome tools.

Data Collection

Time point	Measurement	
Baseline ≤14d from presentation or at presentation	1. Demographic information including gender, age, and BMI 2. Relevant past medical history related to the involved knee including previous surgical procedures, previous intraarticular injections, other treatments, and course of knee pain (i.e., primary osteoarthritis or from previous traumatic injury) 3. Kellgren-Lawrence grade 4. Platelet count -Group A only 5. KOOS subscales 6. NPRS 7. PROMIS Global Health (short form, version 1.1) scale	
RANDOMIZATION – 15 patients per group		
Treatment Delivered ≤30d from Baseline	Group A (n=15) Single episode of BMAC and PRP injections to the target knee	Group B (n=15) Single injection of Gel-One® hyaluronate to the target knee
3 months (+/- 7 days) after treatment	1. KOOS subscales 2. NPRS 3. PROMIS Global Health scale 4. Other relevant therapies received following the study treatment	
6 months (+/- 14 days) after treatment	1. KOOS subscales 2. NPRS 3. PROMIS Global Health scale	

	4. Other relevant therapies received following the study treatment
12 months (+/- 14 days) after treatment	1. KOOS subscales 2. NPRS 3. PROMIS Global Health scale 4. Other relevant therapies received following the study treatment

Risks:

Risks are typical for bone marrow aspiration, blood draw, and intraarticular knee injection and include the following:

Common or likely for blood draw in Group A (participants who will receive BMAC and PRP injections to the target knee):

- Momentary discomfort at the site of the blood draw
- Bruising, redness, swelling, or bleeding at the site of the blood draw
- Feeling of lightheadedness when the blood is drawn

Rare for blood draw in Group A (participants who will receive BMAC and PRP injections to the target knee):

- Infection at the site of the blood draw

Rare for bone marrow aspiration in Group A (participants who will receive BMAC and PRP injections to the target knee):

- Excessive bleeding, particularly in people with low numbers of a certain type of blood cell (platelets)

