- Infection, especially in people with weakened immune systems
- Long-lasting discomfort at the site
- Penetration of the internal organs if the aspiration needle is pushed too deeply into and through the hip bone

Common or likely for Group A (BMAC and PRP injections to the target knee):

- Increased temporary pain at the collection and/or injection site
- Swelling, redness, warmth, stiffness, and/or bruising at the collection and/or injection site

Rare for Group A (BMAC and PRP injections to the target knee):

- Bleeding, infection, reaction to local anesthetic, hypersensitivity or allergic reaction to heparin or anticoagulant sodium citrate

Common or likely for Group B (Gel-One® hyaluronate injection to target knee):

- Increased temporary pain at the injection site
- Swelling, redness, warmth, stiffness, and/or bruising at the injection site
- Hip or knee pain

Less common but serious for Group B (Gel-One® hyaluronate injection to target knee):

- Increased swelling to the knee requiring joint aspiration (removal of fluid)

- Increased pain to the knee requiring an intraarticular steroid injection
- Worsening arthritis related to the injection
- Upper respiratory tract infection

Rare for Group B (Gel-One® hyaluronate injection to target knee):

- Bleeding; infection; muscular weakness; spasms; dizziness; rash; itching; back pain; headache; migraine; high blood pressure; burning sensation; gait disturbance; increased blood liver enzyme, alkaline phosphatase, alanine aminotransferase, urea, and increased or decreased white blood cell count
- Reaction to local anesthetic,
- Allergic/non-allergic reaction to Gel-One® accompanied by cold sweat, paleness, or low blood pressure
- Need for arthroscopy (surgical inspection) of the knee related to the injection

Safety Endpoints:

Patients who experience a significant complication from bone marrow harvest, blood draw, or injection therapy including infection, synovitis with effusion, or excessive pain, will be treated with the appropriate medical intervention. If a patient's platelet count is found to be <150,000 platelets per microliter of blood or >450,000 platelets per microliter of blood after the baseline visit, the patient will be withdrawn from the study and referred appropriately for proper medical follow-up.

Safety Reporting Plan:

The study team or study physician will be responsible for gathering information related to adverse events. The PI will review, evaluate, and monitor AE/SAEs.

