Non-serious adverse events that are considered to be related or possibly related to the research will be reported annually upon IRB renewal. Unanticipated problems that are not adverse events, protocol violations, or enrollment exceptions will be reported within 5 business days from the time the study team received knowledge of the event.

Some adverse events will be expected including those listed as "common or likely", "less common", or "rare" for each treatment group. Other adverse events that are unexpected and are possibly related to the study treatment will be reported within 5 business days of notification of the event. Adverse events that are found to be occurring at a higher rate than expected will be reported within 5 business days of noting a pattern of occurrence. Adverse events that are considered serious, unexpected, and possibly related to the study treatment (i.e., SAEs) will be reported within 1 business day of the notification of the event. SAEs will be reported to the OhioHealth IRB via e-mail reporting using the Adverse Event Template Form, per institutional and national guidelines. SAEs will be tracked for 90 days following notification via chart review.

Recording of Adverse Events:

At each contact with the subject following the treatment intervention, the study team will seek information on adverse events by patient completion of an Adverse Event Collection Form (see Appendix 4.7) and, as appropriate, by examination. Information on all adverse events will be

tracked throughout study participation using the collection form. All clearly related signs, symptoms, and abnormal diagnostic, laboratory or procedure results will be recorded.

The clinical course of each event will be followed until resolution, stabilization, or until it has been determined that the study treatment or participation is not the probable cause.

When an adverse event has been identified, the study team will take appropriate action necessary to protect the study participant and then complete the necessary paperwork and/or log. The primary investigator will evaluate the event and determine the necessary follow-up and reporting required.

Surveys/Questionnaires

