As described previously, the patients’ knee pain, function, and quality of life measures will be assessed via standardized survey tools (i.e., KOOS subscales, NPRS, and PROMIS Global Health scale) at baseline, 3 months, 6 months, and 12 months. The KOOS subscales (i.e., pain, symptoms, activities of daily living, function in sports and recreation, and knee related quality of life) combine for 42 questions in a 5 point rating scale format. The NPRS is a semantic differential scale ranging from zero (i.e., no pain) to ten (i.e., worst imaginable pain). The PROMIS Global Health scale (short form, version 1.1) is a five point rating scale consisting of 10 questions. The patient will independently complete each clinical scale once comprehension is assured. The research team member administering the clinical scales will be available to answer patient questions regarding completing the scale. This research team member will be unaware of group allocation.

Study Calendar

	Study Calendar							
	Presentation	Baseline ≤14d from presentation or at presentation	periodWithdrawal	Treatment ≤30d from Baseline	2-Weeks after treatment +/- 7d	3-Months after treatment +/- 7d	6-Months after treatment +/- 14d	12- Months after treatment +/- 14d
Screen for eligibility	x							
Informed consent		x						
Demographics		x						
Past Medical History		x						
KOOS subscales		x				x	x	x
NPRS		x				x	x	x
PROMIS		x				x	x	x
Other relevant						x	x	x

therapies								
Randomization		x						
CBC (Group A)		x						
Withdrawal ^a			x					
Treatment				x				
Visits	x	x		x	x	x	x	x
SAE Evaluation					x	x	x	x

^aNSAIDs or oral corticosteroids during the 2 weeks leading up to the treatment visit or platelet count <150,000 per microliter of blood or >450,000 per microliter of blood

Data Storage and Confidentiality

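### Adverse events are first sought after the treatment procedure, although randomization, a Group A blood draw and a medication restriction come up to 30 days earlier

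*Combined protocol and SAP*

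**What the plan says.** Four parts of the combined protocol and SAP bear on when adverse events are sought.

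- **Section 2.4, Recording of Adverse Events.** "At each contact with the subject following the treatment intervention, the study team will seek information on adverse events", using a form that the patient completes and, where appropriate, an examination. The next sentence says information on all adverse events will be "tracked throughout study participation using the collection form".
- **Section 2.4, Study Calendar.** The single safety row, "SAE Evaluation", is marked at 2 weeks and at 3, 6 and 12 months. It has no mark at Baseline, the withdrawal period or Treatment.
- **Section 2.4, Safety Reporting Plan.** "The study team or study physician will be responsible for gathering information related to adverse events". No start date is attached.
- **Section 2.4, Study Treatment/Interventions, and section 2.1.** At baseline, Group A patients "will have venous blood sampled by the clinic staff in order to determine the patient's platelet count". For both arms, "All patients will be restricted from use of NSAIDs or oral corticosteroids for 2 weeks prior to the planned treatment procedure". Treatment follows within 30 days of baseline. On losses in that window: "We expect that up to 1 of every 3 patients consented will need to be withdrawn prior to the treatment intervention".

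The Risks subsection lists reactions to the blood draw as expected events in Group A, for example "Feeling of lightheadedness when the blood is drawn".

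**The concern.** Exposure imposed by the study starts at the baseline visit, but the scheduled enquiry starts after the treatment procedure. Two places in section 2.4 give the late start, so it reads as a rule and not a slip of wording. One sentence promises more. A site working from the calendar would not ask about reactions to the baseline draw or problems during the restriction. A patient withdrawn before treatment would reach no visit at which the question is scheduled. The calendar label adds to the doubt: it refers to SAEs, which the Safety Reporting Plan defines narrowly (serious, unexpected and possibly related), while the recording text covers all adverse events.

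Two other parts of the plan depend on this information. The Safety Reporting Plan requires reports of research-related non-serious events and of events seen more often than expected. Section 2.5 promises an intention-to-treat approach for all data, but patients randomized and then withdrawn before treatment would have no solicited safety data to report by arm.

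**Working it through.** **Inputs.** From section 2.1: 30 treated (15 per group), up to 45 consented, up to one third withdrawn before treatment. From section 2.4: treatment within 30 days of baseline; first follow-up at 14 +/- 7 days; last follow-up at 12 months, taken here as 365 days.

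**1. The plan's own figure.** Consented = treated / (1 - withdrawal fraction) = 30 / (1 - 1/3) = 45. This reproduces the stated number.

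**2. Patients with no scheduled enquiry.** 45 - 30 = 15, and 15/45 = 33%. Coverage by at least one scheduled enquiry is 30/45 = 67%. This is the planned maximum, not a forecast.

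**3. Timing for treated patients.** The first marked evaluation falls 14 - 7 = 7 to 14 + 7 = 21 days after treatment, so at the latest 30 + 21 = 51 days after baseline. The pre-treatment window with no enquiry is at most 30 of 365 + 30 = 395 days, or 7.6%.

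**4. Which arm is affected more.** The plan gives no split of withdrawals by arm. Let w of the 15 be in Group A, with 15 treated per arm. The share of each arm with no scheduled enquiry is w/(15 + w) in Group A and (15 - w)/(30 - w) in Group B.

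| w | Group A | Group B |
|---|---|---|
| 0 | 0% | 50% |
| 5 | 25% | 40% |
| 7.5 (equal split) | 33% | 33% |
| 10 | 40% | 25% |
| 15 | 50% | 0% |

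The imbalance can run either way. Platelet-based withdrawal can arise only in Group A, because only Group A has the count. Withdrawal for medication use can arise in both arms.

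**5. How many events could go unasked.** The plan states no event rate, so the rates below are assumptions. With 15 withdrawn patients and a per-patient rate p, the expected number is 15p and the chance of at least one is 1 - (1 - p)^15.

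| Assumed p | Expected | At least one |
|---|---|---|
| 1% | 0.15 | 14% |
| 5% | 0.75 | 54% |
| 10% | 1.5 | 79% |
| 20% | 3 | 96% |

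**6. After the change.** With an enquiry at baseline, treatment and withdrawal, coverage rises from 30/45 to 45/45 and the 30-day window is covered. No sample size or power figure changes.

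**The case against.** The strongest reply is that the plan already provides for early events. Tracking is promised for the whole of participation, the duty to gather information has no start date, research-related events are reportable whether or not they stem from the treatment, and any event once identified must be documented. The enquiry applies at each contact, which need not mean only calendar visits. Patients with an out-of-range platelet count are referred for medical follow-up, which implies some contact at withdrawal. The Adverse Event Collection Form (Appendix 4.7) is not in the available text, so its look-back period is unknown and the 2-week form might reach back to baseline.

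Most of this stands, and it rules out two stronger readings that a reader might infer.

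- *Pre-treatment events are never collected, or never reach the investigator or the IRB.* The text does not say this. Spontaneous or observed events can be logged and reported. What is missing is a scheduled question.
- *Harms are under-counted mainly in Group A.* The documents do not support this. The marrow aspiration and the 60 ml draw for PRP belong to the treatment visit, so their effects fall within the solicited follow-up. The treating physician, who is also the investigator evaluating adverse events, performs the aspiration and the injections. The one Group A procedure before that period is the platelet-count draw, whose listed risks are mostly minor, with infection listed as rare. The medication restriction applies to both arms, and no split of withdrawals is given.

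The reply does not remove the conflict. Two adjacent sentences set different starting points, the calendar follows the later one, and a general duty to gather or log events is not a scheduled enquiry.

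**Conclusion.** The point holds as an internal conflict and a late start to active enquiry. No adverse-event question is scheduled between baseline and treatment, a window of up to 30 days. Up to 15 of 45 consented patients (33%) could leave the study without being asked. Treated patients are first asked, by the calendar, 7 to 21 days after the procedure.

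This rests on the planned maximum withdrawal and on the calendar being followed as printed; the copy in Appendix 4.5 and the form in Appendix 4.7 could not be checked. The direction of any imbalance between arms cannot be determined. No efficacy endpoint or sample size is affected. It should be corrected because it concerns safety ascertainment and costs little.

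**What to change.** 1. In section 2.4, Recording of Adverse Events, replace the restriction to post-treatment contacts with: *Adverse events will be sought from the baseline visit (first study procedure) onward, including at the treatment visit and, for patients withdrawn before treatment, at the time of withdrawal.* This brings the sentence into line with the one that follows it.
2. In the calendar in section 2.4 and its copy in Appendix 4.5, rename the safety row *AE/SAE evaluation* and mark Baseline (after the Group A draw), the withdrawal point and Treatment.
3. State that pre-treatment and treatment-day events will be reported by randomized arm, including patients withdrawn before treatment.

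The cost is protocol wording, two calendar edits, and an existing form completed at visits already planned and at the point of withdrawal. The downside is a few more minor events to log.

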For PRP preparation, 60 ml of venous blood will be withdrawn from either upper extremity by the appropriate clinical staff. The PRP will be handled using a AB60 Pure, Accelerated Biologics 60mL PURE Concentrating System single use disposable kit (Accelerated Biologics, Tequesta, FL, USA).

Ultrasound guided injection procedures:

Sterile probe preparation will be used in addition to routine sterile techniques using chlorhexadine cleansing solution and aseptic technique. All blood handling, harvesting and interventions will be done using strict aseptic protocol.

Group B: (Gel-One® hyaluronate injection to target knee)

Patients will receive a single injection of Gel-One® (Zimmer, Inc., Warsaw, IN, USA) into the target knee. Injections will be performed by the study physician under real-time dynamic ultrasound guidance. Pre-injection aspirations will be carried out if clinically indicated, however, corticosteroids will not be introduced at any time during the trial.

After identifying anatomical landmarks and marking the injection site, the area will be carefully prepared with a chlorhexidine solution, and allowed to dry. Landmarks will then be re-established. The prepared area will be swabbed with alcohol. Skin will be anesthetized with a

vapo-coolant spray for 3-5 seconds. Immediately after evaporation, a needle will be advanced to the target area and safe placement will be achieved with real time ultrasound guidance. Introduction of the injectate (3 ml syringe of Gel-One® - 1% solution [10 mg/mL], 30mg total hyaluronan) will follow without significant resistance or complaints of pain by the patient. The needle will then be withdrawn, the area cleaned, and a band-aid applied.

Following the treatment based on group allocation, all patients regardless of group allocation will be provided and/or will complete the following:

1. A handout will be provided with instructions to follow and tips of what to expect prior to the 2 week visit follow-up with the study physician (see Appendix 4.6).
2. All patients will complete a visit with the study physician to monitor response to joint injection at 2 weeks (+/- 7 days) and 3 months (+/- 7 days) following the treatment date. At the 3 month visit, all patients will also complete the primary and secondary outcome tools with the study staff.

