We recognize that there is risk for inherent bias within our study as patients are unable to be completely blinded to type of treatment he/she receives because each treatment procedure is distinctly different. Risk of selection bias is minimized by use of a randomized allocation schedule. Risk of influence on the patient when completing clinical outcome scales will be negated as the research team member administering the clinical outcome tools at 3, 6, and 12 months post-treatment will be blinded to group allocation.

ClinicalTrials.gov

As this study meets the FDAAA 801 definition of an “Applicable Clinical Trial” based on a drug and biologic, it is required that the study be registered on ClinicalTrials.gov. The Principal Investigator will register and activate the study account prior to enrollment, and all results will be entered upon study completion, followings statistical analysis, per the Results Database Guidelines.

2.5 – Statistical Analysis

Aim 1: Change in mean KOOS subscale scores over time based on treatment group

Total scores will be calculated for each patient using the KOOS subscales. The validated analysis guidelines for the KOOS instrument will be used. Patient’s total scores will be compared at baseline, 3 months, 6 months, and 12 months post treatment and compared by treatment group.

The statistical method that will be used is a Repeated Measures ANOVA (RM-ANOVA). This statistical strategy will allow us to control for the correlation in each individual’s measurements over time. The use of the standardized scales ensures that the outcome variable will be normally distributed, which will meet the underlying assumptions of the RM-ANOVA analysis. We will use the KOOS subscale score as the dependent variable, and the treatment assignment as the independent variable. If the distribution of gender is unequal across treatment groups after randomization, this statistical method will allow us to control for gender because changes in score will differ by gender. We will also be able to control for clinically meaningful variables such as patient age or BMI if there are differences in these variables between the two treatment groups at baseline.

Aim 2a: Change in mean NPRS score over time based on treatment group

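### Blinding the questionnaire administrator cannot negate influence on self-reporting patients who know their procedure, and at 3 months nothing puts the scales ahead of the unblinded physician's review

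*Combined protocol and SAP*

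**What the plan says.** The bias paragraph of Section 2.4 (Dual Enrollment, Risks & Benefits, Bias) makes two statements that bear on each other. It first recognises a risk of inherent bias because "patients are unable to be completely blinded to type of treatment he/she receives because each treatment procedure is distinctly different". It then says: "Risk of influence on the patient when completing clinical outcome scales will be negated as the research team member administering the clinical outcome tools" at the three follow-up assessments will not know the allocation.

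Other parts of Section 2.4 describe who knows what, and when:

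- **Randomization.** "The primary investigator (i.e., the physician providing the treatment) will not be blinded to group allocation". One reason given is the need "to provide the participant with an explanation of the clinical procedure prior to initiating the treatment". The person collecting follow-up variables is to stay blinded throughout.
- **Study Treatment/Interventions, list of follow-up steps.** "All patients will complete a visit with the study physician to monitor response to joint injection at 2 weeks"; the same sentence adds a second such visit at 3 months. The next sentence reads: "At the 3 month visit, all patients will also complete the primary and secondary outcome tools with the study staff". The 6- and 12-month visits are described only as visits for completing the outcome tools.
- **Surveys/Questionnaires.** Patients fill in each scale on their own once they understand it. The administrator is available for questions and does not know the arm.
- **Recording of Adverse Events.** "At each contact with the subject following the treatment intervention, the study team will seek information on adverse events", by means of a form that the patient completes and, where appropriate, an examination.

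Section 2.5 contains no analysis that addresses patients' knowledge of their arm.

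**The concern.** For a self-completed scale, the patient is the assessor. Here the patient knows whether marrow was aspirated and blood drawn, or a single hyaluronate injection was given. Blinding the person who hands over the form removes one source of influence. It leaves the patient's own expectation, and anything the treating physician conveys about how the knee is responding.

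The interpretation of every primary and secondary efficacy comparison is at stake. Section 2.3 describes KOOS as measuring pain, function and quality of life objectively. If the bias paragraph also says that influence on the patient has been negated, a reader of the results could treat an arm difference as free of expectation effects. The design does not have that property. At 3 months there is also an avoidable weakness: physician review and scale completion share a visit with no order set.

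**Working it through.** The disputed statement contains no figure, so the main check is to set the sections side by side.

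**1. Who rates the outcome?** The patient, for KOOS, NPRS and PROMIS alike (Surveys/Questionnaires).

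**2. Does the patient know the arm?** Yes. The physician explains the procedure beforehand (Randomization), the procedures differ visibly (Procedures), and the bias paragraph concedes it.

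**3. Does change from baseline remove the effect?** No. Under Randomization, the team member who schedules treatment learns the allocation only after baseline information has been collected. Expectation tied to the known arm can therefore enter the follow-up scores but not the baseline scores, and subtraction does not cancel it.

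**4. Who else can influence the patient?** The study physician performs both procedures, and Randomization defines the unblinded primary investigator as the physician providing treatment. I therefore read the two as the same person. That person reviews response at 2 weeks and 3 months.

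| Visit | Outcome scales | Physician review specified | Patient knows arm |
|---|---|---|---|
| 2 weeks | no | yes | yes |
| 3 months | yes | yes, order not stated | yes |
| 6 months | yes | no | yes |
| 12 months | yes | no | yes |

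**5. What does the administrator's blind cover?** Only influence from the administrator. It does not act on the last column of the table or on the physician review.

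**6. Illustration of sensitivity (bias sizes assumed, not in the documents).** Take 15 treated patients per arm (Section 2.1), α = 0.05, taken as two-sided because Section 2.2 does not state sidedness, no true effect, and a between-arm reporting difference of b standard deviations. For a two-sample t-test at one time point with complete data:

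- degrees of freedom = 2 × 15 − 2 = 28
- noncentrality = b × √(15/2) = b × 2.739
- rejection rate = P(|T| > t at the 0.975 quantile), with T noncentral t on 28 degrees of freedom

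| Assumed b (SD) | Noncentrality | Rejection rate |
|---|---|---|
| 0 | 0 | 5.0% |
| 0.2 | 0.548 | 8.3% |
| 0.3 | 0.822 | 12.5% |
| 0.5 | 1.369 | 26.2% |

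The two-sided rate is the same whichever arm the bias favours, so the table assumes no direction. It is a simplification of the planned repeated measures ANOVA. It shows only that a modest reporting difference would matter if present, not that one will occur.

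**The case against.** The strongest reply is that the plan already discloses the main bias. The paragraph opens by recognising inherent bias from incomplete patient blinding, and the disputed sentence can be read narrowly as concerning influence from the person in the room. On that reading, blinding that person and letting patients complete the scales independently is a reasonable safeguard. Part of this stands: the plan does not hide the problem, and the administrator's blind is worth having. But the sentence speaks of influence on the patient without limiting its source, and *negated* is too strong under any reading that includes the patient's own knowledge or the physician.

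A second reply also stands in part. The physician review shares a visit with the scales only at 3 months, whereas Hypothesis 1 places the between-arm KOOS advantage at 6 and 12 months. At 3 months it predicts improvement in both arms relative to baseline. Same-visit contact therefore bears on the 3-month KOOS comparison listed in Aim 1 and on the 3-month NPRS and PROMIS hypotheses (2a and 2b), but not directly on the main KOOS hypothesis.

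A reader might also infer that adverse event collection unblinds the administrator, because a complaint about the marrow site reveals the arm. The documents do not show this. The patient completes the form, the study team or study physician gathers the information, and no section says that the blinded collector takes or reads it. Collection-site pain is listed as temporary and long-lasting discomfort as rare, while the scales are first repeated at 3 months. Disclosure is possible, which justifies a simple precaution and no more.

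**Conclusion.** The point holds in a limited form. The statement that influence on the patient is negated is wrong as written, because every efficacy outcome is self-reported by a patient who knows the procedure. That applies at 3, 6 and 12 months. The absence of an order between physician review and scale completion is a separate, smaller gap that applies to 3 months only. It rests on reading the study physician and the unblinded primary investigator as one person.

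The size and direction of any bias cannot be derived from the documents. A reader might assume that expectation favours the novel treatment by some share of the 10-point KOOS threshold. The documents give no such figure, and they present the 10 points as a minimal important change in a subscale score, not as a between-arm difference. The rejection rates above are conditional on assumed biases. Nor does the finding imply that the trial should have blinded patients or that its comparisons are uninformative. It concerns an overclaim and an inexpensive missing safeguard.

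**What to change.** 1. **Visit order (Section 2.4, follow-up steps and Study Calendar).** Require KOOS, NPRS and PROMIS to be completed before any physician contact at the 3-month visit, and before the adverse event form at 3, 6 and 12 months. Ask patients not to tell the collector which treatment they received.
2. **Wording (Section 2.4, bias paragraph).** Replace *negated* with *reduced*. State that between-arm differences in these self-reported outcomes may include expectation effects at all time points.

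The cost is a small constraint on the order of activities within visits and a less favourable statement about bias. Neither change needs new staff, extra visits or a new instrument, and neither alters which adverse events are collected. The changes do not remove patients' knowledge of their arm or the effect of the earlier 2-week physician visit, which is why the second change is needed as well as the first.

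A baseline expectation question is not recommended. Expectation measured before allocation should be balanced by randomisation, and it would not capture what arises once patients learn their arm. A separate person to collect the adverse event form is not needed on the evidence in the documents.
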